2.8.7 Safety evaluation during the Safety follow-up

Safety data collected after last administration of study drug includes adverse events, vital signs, routine laboratory parameters, laboratory assessments to measure total IgG, total IgM, B-cell repletion and residual teriflunomide PK levels, and eCSSRS. No safety cutoff date will be applied in the analyses defined in this section. Safety data within the safety cutoff date but after last administration of study drug will also be included.

The number and percentage of patients with at least one TEAEs that started after the date of last administration of study drug will be reported by SOC, preferred term, and treatment group. The subset of patients in SAF who had data reported after the date of last administration of study drug will be included in the analysis and the number of patients in this subset will be the denominator in calculating the percentage.

The vital signs data collected after study drug discontinuation will be summarized as summary statistics of the vital sign measures and of the change from baseline in the vital sign measures by treatment group for each visit-window after study drug discontinuation (as defined in [Section 2.1.2.2](#)). The SAF will be used for these analyses.

The B-cell counts and its change from baseline values will be summarized by treatment group for each visit-window after study drug discontinuation. In addition, the change from last assessment on study drug in B-cell count will also be summarized similarly. Graphic presentation of B-cell counts distribution will also be provided by treatment group for each visit-window after study drug discontinuation. Additionally, number and percentage of patients with B-cells within 10%, 10 to 20%, 20 to 50%, 50% to 80%, 80 to 100% of baseline, or with B-cells < the lower limit of normal (LLN), or with B-cell repletion will be presented by treatment group for each visit-window after study drug discontinuation. B-cell repletion is defined as B-cell counts having returned to their baseline value or to LLN (i.e., $\geq 100\%$ of baseline or $\geq \text{LLN}$). The analysis will be limited to the subset of patients in SAF who had B-cell count data after the date of last administration of study drug; the number of patients in this subset will be the denominator in calculating the percentage.

Patients with teriflunomide plasma data will be listed as only small percentage of patients are expected to have such data.

The eCSSRS data collected after study drug discontinuation will be summarized similarly as in [Section 2.8.6](#). The subset of patients in SAF who had at least one eCSSRS performed after the date of last administration of study drug will be included in the analysis and the number of patients in this subset will be the denominator in calculating the percentage.

As stated in [Section 2.1](#), the registration CSR will contain only partial data collected from the Safety FU epoch because the registration CSR cutoff date will depend on EOS date of the study. A complete analysis of the post-treatment safety follow-up will be provided in the final CSR when all patients have completed the Safety FU epoch.

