End of treatment (EOT) visit is not mandatory for all patients. It is only applicable to patients who prematurely discontinue double-blind study treatment and will continue to follow the assessment schedule of the Treatment epoch (Table 6-1).

End of study (EOS) visit is mandatory for all patients. The EOS Visit is conducted at the end of the Treatment epoch (i.e. when the patient has completed up to 30 months, or when EOS is declared for all patients, or at time of premature withdrawal from study). At the time EOS is declared for all patients, all patients ongoing in the Treatment epoch should be contacted and their EOS Visit should be scheduled to occur as soon as possible.

Patients who prematurely discontinued study drug but do not agree to continue to be followed in the study Treatment epoch per Table 6-1, but agree to continued safety follow up, will have their EOS Visit and then enter the Safety Follow-up (FU) according to schedule in Table 6-2 .

Patients who complete the Treatment epoch on study drug but do not enter the Extension study, will have their EOS Visit and then enter the Safety Follow-up (FU) schedule in Table 6-2.

During the study, patients will be asked to complete a diary from Month 1 onwards to record information pertinent to study drug administration (including date and time of sc injections) and home pregnancy testing (date and results) for females of childbearing potential. The patient is requested to bring the completed diaries with them to each visit and the Investigator/Study Nurse/Study Coordinator must review these for completeness and for potential AEs, injection related reactions, study drug interruptions etc. and record information obtained from the diaries on the relevant CRFs.

A structured telephone interview script provided for the study will be conducted by site personnel every month starting at Month 2 (Table 6-1). The interview should take place around time of the monthly sc self/home-injection to query about any new or worsening symptoms

warranting an unscheduled visit, injection reactions, and, as applicable, results of home pregnancy testing, compliance with contraception requirements and with any scheduled local LFT lab testing.

Some protocol procedures may be done via an outpatient setting (e.g. at patient's home) with the support of study staff or a healthcare professional registered with the study site for the study, if this is permissible per the local regulatory authority.

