2.1.1 General definitions

Below summarize some general definitions to be used in the rest of the document.

Table 2-1 **general definitions**

Study treatment/Study drug	Both the investigational drug (ofatumumab) and the active comparator (teriflunomide) will be referred as study treatment or study drug.
Actual treatment	Actual treatment patients received. Ideally, actual treatment should be the same as randomized treatment. It could be different in case study drug is mis-dispensed. If patients received both investigational drug and active comparator accidentally during the study, their actual treatment will be the treatment to which they were exposed longer in duration. For safety analysis, patients will be analyzed according to the actual treatment received.
Date of first administration of study drug/first dose date	The first dose date of active study drug administration. For determining this date, matching placebo dummy treatment records will be excluded.
Date of last administration of study drug/last dose date	The last dose date of active study drug administration. For determining this date, matching placebo dummy treatment records will be excluded.

Study Day 1 or Day 1	The date of first administration of study drug/first dose date.
Study Day	All other study days will be labeled relative to Day 1. For events with dates on or after Day 1, study day for the event is calculated as (event start date – first dose date + 1). For events with dates before Day 1, study day for the event is calculated as (event start date – first dose date). Day 0 will not be used.
Duration of an event	Duration of an event is calculated as (event end date – event start date +1).
1 month	30 days; to be used in defining 3-month or 6-month confirmed disability worsening or improvement.
4 weeks	28 days; to be used in determining target days of scheduled visits. It is based on the scheduled injection frequency for ofatumumab (during the maintenance phase).
Day post-study drug discontinuation	Day post-study drug discontinuation for a particular event is calculated as (event start date – study drug discontinuation date).

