 - Black or African American: those who selected “Black” as race on demography CRF

- Other: those who selected “Native American” or “Pacific Islander” or “Unknown” or “Other” as race on demography CRF
- *Patients who accidentally received both investigational drug and active comparator during the study
- **Patients in SAF who had data reported after date of last administration of study drug
- **Patients in SAF who had at least one eCSSRS performed after the date of last administration of study drug
- **Patients in SAF who had B-cell count data after the date of last administration of study drug
- **Patients in SAF who had teriflunomide data

*This subgroup will be used for exploratory analysis described in [Section 2.8.1](#). **These subgroups will be used for corresponding safety follow up data analysis described in [Section 2.8.7](#). Rest of the subgroups will be used for patient-year summaries described in [Section 2.4.1](#).

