2.4 Treatments (study treatment, rescue medication, concomitant therapies, compliance)

2.4.1 Exposure to study treatment / compliance / time at risk

Duration of exposure to study drug will be derived as follows:

- For patients whose actual treatment ([Section 2.2](#) Safety set) is teriflunomide, duration of exposure will be calculated as (last dose date – first dose date +1 - Σ [number of days with temporary study drug interruption]), which is the number of days between the first and the last day of study drug administration, excluding the number of days with temporary study drug interruption (as patients are scheduled to take the oral study medication once daily).
- For patients whose actual treatment is ofatumumab, duration of exposure will be calculated as (last injection date – first injection date + 31 – Σ [(j+1)th injection date – jth injection date -31]), where j and j+1 refer to consecutive injections with injection dates more than 31 days apart (as patients are scheduled to take the subcutaneous injections every 28 +/- 3 days).

Duration of exposure to study drug will be summarized descriptively on SAF set by treatment group and duration category (i.e., ≥ 1 week, ≥ 2 weeks, ≥ 3 weeks, ≥ 4 weeks, ≥ 8 weeks, ≥ 12 weeks, ≥ 24 weeks, ≥ 36 weeks, ≥ 48 weeks, ≥ 60 weeks, ≥ 72 weeks, ≥ 84 weeks, ≥ 96 weeks, ≥ 108 weeks, ≥ 120 weeks, ≥ 132 weeks, ≥ 144 weeks, ≥ 156 weeks, ≥ 168 weeks). Descriptive statistics of duration in days will also be provided by treatment group.

For each treatment group, the number of patient-years is calculated as (the sum of the number of days of exposure for all patients in the group)/365.25 and will be summarized by age and gender, by gender and weight, as well as by race. Cutoffs for age subgroups and weight subgroups are defined in [Section 2.2.1](#).

Time at risk is the censoring time used for estimating exposure adjusted incidence rate of SAEs or AEs in patients who did not experience the event of interest. For patients who have experienced the event of interest, the actual date of the SAE, or AE onset will be used. Details

about the calculation of exposure adjusted incidence rate of adverse events are described in [Section 5.7.2](#). Time at risk also corresponds to the time period used for adverse event reporting.

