5.1 Imputation rules

5.1.1 Study drug

Missing or partial dates are not allowed in completing the study drug administration CRF pages. The end date of study drug will be the last end date or last injection date for patients randomized to teriflunomide or ofatumumab, respectively.

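### Minor: adverse events starting after last dose are summarised only as crude percentages (SAP 2.8.7); add a rate with its clock at last dose and report post-dose follow-up time by arm

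*SAP*

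**What the plan says.** SAP 2.8.7 (Safety evaluation during the Safety follow-up) reports "The number and percentage of patients with at least one TEAEs that started after the date of last administration of study drug" by system organ class, preferred term and arm. The denominator is a head count: "The subset of patients in SAF who had data reported after the date of last administration of study drug will be included". SAP 2.2.1 lists the same subset as a safety subgroup. No safety cut-off applies in 2.8.7, and days 1 to 100 after last dose are included. The section plans no rate and no summary of post-dose follow-up time.

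Last dose is dated on active drug alone. SAP 2.1.1 defines it as "The last dose date of active study drug administration. For determining this date, matching placebo dummy treatment records will be excluded". SAP 5.1.1 adds: "The end date of study drug will be the last end date or last injection date for patients randomized to teriflunomide or ofatumumab, respectively".

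SAP 2.8.1 adds exposure-adjusted incidence rates for any TEAEs and for serious TEAEs, giving flexible follow-up as the reason. Under SAP 2.4.1 and 5.7.2 those clocks start at first dose. Time at risk for AEs ends at last dose plus 100 days. Time at risk for SAEs runs to end of study including Safety Follow-up.

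**The concern.** A crude percentage compares arms fairly only when patients are observed for similar lengths of time. After last dose that is not assured here, for four reasons.

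- **Dosing interval.** Ofatumumab is injected every 28 days (± 3 days) and teriflunomide is taken daily (Protocol 5.5.4). When End of Study is declared, "all patients ongoing in the Treatment epoch should be contacted and their EOS Visit should be scheduled to occur as soon as possible" (Protocol section 6), and Table 6-1 shows no dispensing at that visit. It can fall anywhere in the injection cycle. An ofatumumab completer may then be days to weeks past last dose, and a teriflunomide completer about a day past or not past at all.
- **Extension entry.** Completers who enter the Extension do not enter Safety Follow-up, so these short tails are all they contribute to the table.
- **Prolonged follow-up.** Monitoring beyond 9 months is triggered by unrepleted B-cells or by teriflunomide above 0.02 mg/L. It does not go beyond 9 months if another disease-modifying or immunosuppressive therapy has been started before then (Protocol 3.1).
- **Report timing.** The registration report contains only partial Safety Follow-up data (SAP 2.8.7).

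At stake is the reading of the one by-arm adverse event table specific to the time after stopping a long-acting B-cell depleter. No confirmatory result depends on it.

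**Working it through.** **1. Do the planned rates already cover this?** The plan gives no figure to reproduce, so this is a comparison of clocks.

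| Planned summary | Clock starts | Clock ends |
|---|---|---|
| AE rate (2.4.1, 2.8.1, 5.7.2) | first dose | last dose + 100 days |
| SAE rate (same sections) | first dose | end of study, including Safety Follow-up |
| Post-dose TEAE table (2.8.7) | day after last dose | open; no rate |

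Non-serious TEAEs after day 100 have no rate. Serious TEAEs after day 100 have one that mixes on-drug and post-drug time. Nothing isolates the post-dose period.

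**2. Where does the dosing interval belong?** SAP 2.4.1 states: "For patients whose actual treatment is ofatumumab, duration of exposure will be calculated as (last injection date – first injection date + 31", less any gaps. That credits 30 days after the last injection as exposure. The teriflunomide formula adds 1 and so credits none. Section 2.8.7 counts those same 30 days as post-dose.

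**3. Illustration of the mechanism.** The documents do not give these shares for this trial. Assumptions:

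- 450 patients per arm and the same constant rate, r = 1 event per year, in both arms;
- 27% stop early (the figure from one earlier teriflunomide trial, Protocol 9.8.1.1) and are followed 1 year;
- 80% of completers enter the Extension, and other completers are followed 0.75 years;
- the EOS visit falls 14 days after the last injection, or 1 day after the last capsule.

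Numbers per arm: early stoppers 450 × 0.27 = 121.5; other completers 450 × 0.73 × 0.20 = 65.7; Extension entrants 450 × 0.73 × 0.80 = 262.8. A patient observed for t years has an event with probability 1 − exp(−r·t).

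- Ofatumumab: 121.5 × (1 − e^−1) + 65.7 × (1 − e^−0.75) + 262.8 × (1 − e^(−14/365.25)) = 76.8 + 34.7 + 9.9 = 121.4; 121.4/450 = **27.0%**.
- Teriflunomide, half of Extension entrants having data after the last capsule: 76.8 + 34.7 + 0.4 = 111.8 (unrounded terms); 111.8/318.6 = **35.1%**.
- Teriflunomide, all of them having such data: 112.2/450 = **24.9%**.

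The sign reverses when about 87% of teriflunomide entrants have such data. The rate D/T, with the clock at last dose, is 1.0 per year in both arms throughout.

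**4. Range.** Inputs varied: 20–30% stopping early, 50–90% entering the Extension, 0.5–1.5 events per year, a 7–28 day gap, and 9–18 months of follow-up for early stoppers. Teriflunomide minus ofatumumab is then +2.3 to +12.9 points (half) or −7.5 to −0.3 points (all). At 0.1 events per year, nearer a single preferred term, it is +0.6 to +2.0 or −0.5 to −0.06 points.

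**5. A second route, unequal prolongation.** With 270 versus 360 days of follow-up (assumed) and an equal rate of 0.2 per year, the crude figures are 1 − exp(−0.2 × 270/365.25) = 13.7% and 1 − exp(−0.2 × 360/365.25) = 17.9%. The D/T ratio is again 1.00.

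**6. Registration report.** Suppose no Safety Follow-up visit has yet occurred, so all 328.5 completers have only the gap days. Ofatumumab is (76.8 + 12.4)/450 = 19.8%. Teriflunomide is 77.3/285.8 = 27.0% (half) or 77.7/450 = 17.3% (all).

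**The case against.** Several points on the other side stand.

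- **Post-dose time is partly recoverable.** SAP 2.4.1 summarises both times at risk by arm. Per arm, SAE time − (AE time − 100 days × n) gives aggregate post-dose time. A reader might infer that nobody could correct the crude table; at the final report a rough correction is possible. It fails at the registration report, where cut-off truncation breaks the subtraction, and it never gives time to first event by preferred term. Numbers per post-dose window for vital signs and B-cells (SAP 2.1.2.2, 2.8.7) add a rough picture only.
- **Much is covered elsewhere.** TEAEs to day 100 and serious TEAEs at any time already enter exposure-adjusted rates, all AEs are listed, and the table shows its denominators.
- **Rates assume constant risk.** SAP 2.8.1 itself reserves them for events with constant risk over time, which washout may not satisfy. If the rate is 1.0 per year to 9 months and 0.5 after, early stoppers followed 12 months in the ofatumumab arm and 15 months in the teriflunomide arm (half case) give 0.94 and 0.90 per year from an identical hazard. A split at 100 days would lessen such effects but not remove this one.
- **Direction is unknown.** A reader might infer that the table will favour one named drug. The documents do not support that, because the sign turns on a share they do not give. Nor do they support a scenario in which no teriflunomide Extension entrant has later data, since "End of study (EOS) visit is mandatory for all patients".
- **Excluding Extension entrants is not a sound remedy.** It needs an entry flag the core documents do not describe, and it selects on a choice made after randomisation by patients who completed on drug.

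**Conclusion.** The point holds as a minor, inexpensive improvement. On the text, SAP 2.8.7 offers only crude percentages over a follow-up period whose length varies by design and can differ by arm, and no planned rate isolates that period. The SAP's own reason for adding rates in 2.8.1, flexible follow-up, applies equally here.

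The size of any distortion is unknown. Under the assumed inputs it runs from a fraction of a point for uncommon events to about 13 points for any event, in either direction. Those figures rest on an equal constant rate in both arms and on unsourced shares for Extension entry and for post-capsule data. They show that the artefact can arise, not that it will. The primary, key secondary and main adverse event tables are unaffected.

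**What to change.** Keep the crude table in SAP 2.8.7 and add:

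1. Exposure-adjusted incidence rates and rate ratios by the SAP 5.7.2 method. Time at risk runs from the day after last dose to first event, or otherwise to the end of core-study follow-up (including Safety Follow-up) or the analysis cut-off. Split by interval, for example 0–100 days and over 100 days. Add a sensitivity version that starts the ofatumumab clock 30 days after the last injection, matching the exposure definition in SAP 2.4.1.
2. A by-arm summary of post-dose follow-up time.

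The cost is SAP wording, one extra table set using a method already specified, and one follow-up summary. The end-of-follow-up date needs an explicit definition. The rates assume roughly constant risk within each interval, so they should be read beside the crude table rather than in its place.

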2.9 Pharmacokinetic endpoints

2.9.2 Immunogenicity assessment

Samples will be analyzed for the presence of human anti-drug antibodies (ADA). The data will be summarized by visit and overall (i.e. proportion of patients with ADA) as an assessment of the immunogenicity potential of ofatumumab. A listing by patient will also be provided. All patients in FAS with non-missing values will be included in these analyses.

2.10 PD and PK/PD analyses and modelling

PK concentration data summarized by visit together with by-patient listings will be provided in the study report. All patients in FAS with non-missing values will be included in these analyses.

2.11 Patient-reported outcomes

For patient-reported outcomes, data from unscheduled visits will not be summarized but will be listed only. The FAS will be used for all analyses of patient reported outcomes.

[figure not shown]
2.11.1 MSIS-29

[figure not shown]
The Multiple Sclerosis Impact Scale version 2 (MSIS-29 v2) is a 29-item, self-administered questionnaire that includes two domains, physical and psychological. The questions in the scale ask the patient for their views about the impact of MS on their day-to-day life during the past two weeks. Each of the 29 items will be given a score between 1 (not at all) and 4 (extremely) (MSIS-29 v2 guidelines). The physical impact score is computed by summing up Items 1-20 (resulting in a score between 20 and 80). The psychological impact score is computed by summing up Items 21-29 (resulting in a score between 9 and 36).

[figure not shown]
For ease of interpretation, these scores are transformed to a scale of 0-100 using the following formula: $100 \times (\text{observed score} - \text{lowest possible score}) / (\text{highest possible score} - \text{lowest possible score})$. The higher the score, the greater is the degree of disability.

In case of missing item scores, the following rule applies: if more than 50% (i.e., more than 10 for the physical scale and more than 4 for the psychological scale) of the item scores are missing, the scale score will not be calculated and set to missing. If no more than 50% of the item scores are missing, the scale score will be imputed as the average of the non-missing item scores multiplied by the number of items in the scale (20 for the physical scale and 9 for the psychological scale).

Both the MSIS-29 physical impact score and the psychological impact score and the corresponding changes from baseline will be summarized by visit-windows. The change from baseline at post-baseline visit-windows will be compared between treatment groups using a repeated measures mixed effects analysis adjusted for treatment, visit-windows (as class variable), region, and the corresponding baseline score.

2.14 Interim analysis

Two separate SAPs will be developed to document methodology details, one for analyses that will be performed for DMC (as mentioned in [Section 2.14.2](#)), the other for analyses that will be performed for blinded data reviews (as mentioned in [Section 2.14.3](#)).

2.14.1 Unblinding interim analysis

No unblinding interim efficacy analysis is planned for this study.

